4.3 Follow- up procedures (by visits)

Following the conclusion of the trial, all participants will be provided with referral information as appropriate for further treatment.

4.4 Unscheduled visits

N/A

4.5 Concomitant Medication documentation

At study entry, subjects may not have taken any psychotropic medications in the past 4 weeks (8 weeks for fluoxetine). At each therapy visits participants will be asked to report any medications they may have initiated, and any psychotropic medication use will be exclusionary. Concomitant medications will be documented in RedCap.

4.6 Rescue medication administration (if applicable)

N/A

4.7 Subject Completion/ Withdrawal procedures

Completion: Participants will complete the study after 15 weekly treatment sessions.

Withdrawal procedures. Patients may opt to discontinue participation at any time. Any patient who misses three consecutive scheduled appointments will be a dropout, and this will be explained to patients during consent and whenever a patient begins missing sessions. This operational definition of dropout will be used in data analyses.

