11. Psychotropic medication use in the past 4 weeks (8 weeks for fluoxetine) and/or current psychotherapy. Participants must be medication-free at study entry; study personnel will not supervise medication taper for the purpose of the study, but those who taper under the supervision of their regular provider will be eligible;
12. Currently pregnant, as measured by urine pregnancy screen immediately before MRI scans;
13. Positive urinalysis screen for cocaine, marijuana, opiates, methadone, amphetamines, and benzodiazepines (conducted on-site via Biosite Triage Meter Plus) at study entry.
14. No neurological conditions (e.g., history of stroke, seizure, or TBI);
15. Contraindications for 7T imaging (criteria are more stringent than for 3T imaging): Metal in the body, dental work that is not fillings or gold, any tattoos, any metal in the body, any metal injury – especially those to the eyes, any other type of implant unless they are 100% plastic.

Number Of Subjects	60 subjects will be randomized such that half will receive BATA and half will receive MBCT.
---------------------------	---

Study Duration	Approximately 16 weeks
Study Phases	(1) Phone/online Screening : initial screening for eligibility.
Screening	(2) In-Person Screening : further screening for eligibility and consent
Study Treatment	(3) Baseline fMRI
Follow-Up	(4) Initiate up to approximately 15 weeks of therapy (experimental treatment (BATA) or comparison treatment (MBCT)) (5) Mid-treatment fMRI scans at approximately weeks 8 and 12. (6) Post-treatment fMRI scan.
Efficacy Evaluations	(1) fMRI activation in right CN during reward anticipation and rACC during reward outcomes (2) Anhedonia severity (SHAPS scores)
Pharmacokinetic Evaluations	N/A
Safety Evaluations	1) 7T MRI safety screening form completed before each scan session 2) Columbia-Suicide Severity Rating Scale (C-SSRS) completed if a subject endorses suicidal thoughts at therapy visits.

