6.4 Statistical Methods

Aim 1, fMRI outcomes: Only patients who complete at least two therapy sessions will participate in post-treatment assessments. We will compare fMRI activation in regions of interest at pre- and post-treatment. The design is a 2 (BATA vs MBCT) X 2 (CN, rACC) X 2 (pretreatment vs post-treatment) ANCOVA testing the change from pre- to post-treatment as moderated by treatment group and brain region in the outcome variables. The Treatment × Time interaction beta will be used to evaluate whether BATA produces changes in neural responses to reward anticipation and reward outcomes that exceed our *a priori* target engagement criteria (increased right caudate nucleus (CN) activation during reward anticipation and decreased rostral anterior

cingulate cortex (rACC) activation during reward outcomes) and exceed changes due to MBCT. *Post-hoc* comparisons will compare change across each region.

Aim 2, anhedonia outcomes: To evaluate the effects of BATA, relative to MBCT, for on anhedonia symptoms treating anhedonia, we will test for differential change over time between those who receive BATA and those who receive MBCT post-treatment. We will use an intent-to-treat (ITT) analysis for patients who receive BATA relative to those who don't. The ITT model will be a repeated-measures ANCOVA with effects for treatment condition (BATA, MBCT), outcome measure (SHAPS), time (pre-treatment, post-treatment) and their interactions. The interaction tests will assess mean differences at each time point as well as differences in the degree of change between the groups. This also provides tests of each group relative to their baseline scores. We will include gender and age as covariates in these models.

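### Dropout status after three consecutive missed appointments is given an unstated role in the analyses and is not reconciled with the two-session rule or the Aim 2 intent-to-treat label

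*Combined protocol and SAP*

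**What the plan says.** Section 4.7, under withdrawal procedures, states: "Any patient who misses three consecutive scheduled appointments will be a dropout". No number of sessions already attended changes this. The rule is to be explained to patients at consent, and the paragraph closes with "This operational definition of dropout will be used in data analyses". The same section defines the other end of the course: "Participants will complete the study after 15 weekly treatment sessions".

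Section 6.4 sets another attendance condition, under Aim 1: "Only patients who complete at least two therapy sessions will participate in post-treatment assessments". The synopsis repeats it. Section 6.4 does not refer to the dropout definition.

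For Aim 2 only, section 6.4 says: "We will use an intent-to-treat (ITT) analysis for patients who receive BATA relative to those who don't". The model is a repeated-measures ANCOVA on the pre-treatment and post-treatment SHAPS. Neither aim has a missing-data method, and Aim 1 has no analysis set beyond the two-session condition.

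**The concern.** Take a patient who attends eight sessions and then misses three appointments. Under 4.7 this patient is a dropout, and that status is to be used in the analyses. Under 6.4 the same patient satisfies the attendance condition for post-treatment assessment. The plan does not say whether the patient is still invited to the scan and SHAPS, or whether the data enter the models. One team could stop assessing such patients and another could keep them, both citing the plan, and the choice could be made after data are seen.

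The choice matters because attendance follows randomisation and may be related to outcome. The protocol itself describes anhedonia as a loss of motivation (section 1.1). The two therapies also ask different things of patients: section 1.2 asks the MBCT arm for 30 minutes of home meditation a day, and reduces monitoring effort in BATA for patients with low motivation. If dropouts were left out, the arms compared would no longer be the arms randomised. This group also differs from those with fewer than two sessions, so repairing the two-session rule alone would not settle what happens to it.

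**Working it through.** **The plan's own figure.** There is none to reproduce. Section 6.5 gives no dropout rate and no allowance for dropout. Everything below is for scale and rests on assumed rates.

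**Inputs from the documents.** The rule needs three consecutive misses (4.7). There are 15 weekly sessions (4.7). Sixty patients are randomised equally, so 30 per arm (synopsis). Assessment requires at least two sessions (6.4).

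**Assumptions.** Scheduled appointments are taken to be the 15 therapy sessions. Each is missed independently with probability p. Clustered absences would raise the figures.

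**Step 1: how many meet the rule.** Let F(n) be the probability of a run of three misses by session n. Then F(0) = F(1) = F(2) = 0, F(3) = p³, and F(n) = F(n−1) + [1 − F(n−4)](1−p)p³. For p = 0.2, F(3) = 0.008 and each later step adds at most 0.8 × 0.008 = 0.0064. F(15) therefore cannot exceed 0.008 + 12 × 0.0064 = 0.085, and the full recursion gives 0.083.

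**Step 2: how many of these already had two sessions.** The same recursion is run while counting the sessions attended before the run.

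| p | Meet the rule | Of 60 patients | Share with ≥2 sessions before the run |
|---|---|---|---|
| 0.10 | 1.2% | 0.7 | 83% |
| 0.20 | 8.3% | 5.0 | 81% |
| 0.30 | 23.7% | 14.2 | 77% |

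At p = 0.20 about 0.81 × 5.0 = 4 patients would satisfy the condition in 6.4 and still be dropouts under 4.7. At p = 0.30 it would be about 0.77 × 14.2 = 11.

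**Step 3: bias, if dropouts were excluded.** If a fraction f of an arm drops out and their mean outcome is Δ worse than that of the patients who stay, the remaining patients overstate the arm mean by fΔ. The bias in the difference between arms is f₁Δ₁ − f₂Δ₂. With 20% versus 10% dropout and the same Δ in both arms:

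- Δ = 0.5 SD: (0.20 − 0.10) × 0.5 = 0.05 SD
- Δ = 1.0 SD: (0.20 − 0.10) × 1.0 = 0.10 SD

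With equal f and equal Δ the terms cancel. A simulation of 5,000 null trials agrees (30 per arm, two-sided 0.025, assumed correlation of 0.5 between outcome and staying). With 20% dropout by the same mechanism in both arms, the bias was 0.002 SD and the type I error 0.023. Equal rates alone are not enough: with 30% dropout in each arm, related to outcome in one arm only, the bias was 0.25 SD and the type I error 0.075.

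**Step 4: set against the planned effect.** Section 6.5 expects effects from 0.75 upwards, labelled z. Read as a standardised mean difference, which is an assumption, a bias of 0.05-0.10 SD is 0.05/0.75 = 7% to 0.10/0.75 = 13% of the smallest planned effect.

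**The case against.** The strongest objection is that no sentence excludes anyone. Counting dropouts by arm is also a use in data analyses, and section 6.3 treats adherence and dropouts as something monitored and reported to the DSMB. A reader might infer from 4.7 that attendance decides who is analysed. The documents permit that reading but do not state it.

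Second, Aim 2 is labelled intent-to-treat. Followed, that keeps dropouts in the SHAPS comparison, so it would be wrong to say that the plan builds selection into the SHAPS result. The label is loosely worded, in terms of who receives BATA, but nothing shows that 4.7 overrides it.

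Third, a reader might infer that 6.4 promises assessment to everyone with two sessions, so that 4.7 flatly contradicts it. The word used is only, which sets a necessary condition. The two rules can coexist.

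Fourth, the figures depend on assumed rates and on exclusion.

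All four objections stand, and they limit the claim. They do not remove it. The rule sits among the withdrawal procedures and is expressly given an analytic use. Aim 1, the primary comparison, has no intent-to-treat statement. The Aim 2 label cannot supply a post-treatment SHAPS that was never collected.

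**Conclusion.** The point holds as an unresolved rule with a possible bias, not as a stated exclusion. The plan assigns dropout status a role in the analyses without saying what it is, uses a different attendance condition in 6.4, and protects only Aim 2 by label. Read as withdrawal or exclusion, the rule would let attendance after randomisation help determine the primary fMRI comparison.

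On assumed rates the group is anywhere from about 1 to 14 of 60 patients, and most of them would already meet the two-session condition. Conditional on exclusion, a modest imbalance (20% versus 10%) gives a bias of about 0.05-0.10 SD. It is about zero if dropout is equal and arises in the same way in both arms. Its direction depends on which arm loses more patients and how they fare. This is worth correcting before analysis, but the documents do not show that the results would be biased.

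**What to change.** In section 4.7, define dropout as a description of therapy attendance, reported by arm, and state that it is not a criterion for any analysis set. State that patients who meet it are still invited to the scheduled SHAPS and scans unless they withdraw consent.

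In section 6.4, state that all available data enter the Aim 1 and Aim 2 models in the randomised arm. Name a likelihood-based repeated-measures model that uses patients who lack a post-treatment value, with its missing-at-random assumption stated. The week 8 and week 12 scans and SHAPS already in the schedule could inform it. Show an analysis without dropouts only as a sensitivity analysis. Reconcile 4.7, the two-session condition and the intent-to-treat wording so that they describe one set of patients.

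The cost is mostly wording, plus some extra contact effort, scans for patients who have stopped attending (some will decline) and a change to how the dropout rule is explained at consent. The change concerns assessment and analysis only, not whether therapy continues.

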4.8 Screen failure procedures

If more than 4 weeks elapse between the baseline screen and the first scan session, this will be considered a screen fail and the individual will not be randomized.

5 STUDY EVALUATIONS AND MEASUREMENTS (how measurements will be made)

1) fMRI data (primary endpoint) will be collected at the UNC Biomedical Research Imaging Center (BRIC) at week 0, week 8, week 12, and week 15. Analyses of fMRI target engagement will focus on activation in the right CN during reward anticipation, the rACC during reward outcomes, and bilateral amygdala in response to threat. Data will be preprocessed using FSL (Oxford University, UK). We will ensure groups do not differ in head motion by calculating mean framewise displacement which yields, for each participant, a value indicating mean head displacement from one volume to the next. Hypotheses will be evaluated with a ROI approach whereby signal intensities are extracted from ROIs for the relevant task contrasts (i.e., potential win versus non-win trials during MID reward anticipation trials; wins versus non-wins during MID reward outcome trials; fearful and angry faces > shapes during the threat task). ROI analyses will be followed-up with whole-brain analyses that will yield activation maps thresholded at a False Discovery Rate of 0.01 to allow for an examination of activation in other reward processing regions, including the ventral striatum/nucleus accumbens, putamen, ventral tegmental area, and orbitofrontal cortex. To optimize BOLD signal coverage in the ventral

tegmental area we will acquire high-resolution T1-weighted images with 1x1x1 mm voxel size to allow for precise registration and will use cardiac and respiratory gated imaging during the acquisition of structural scans to address pulsatile artifacts using retrospective corrections implemented with the FSL PNM toolbox.

2) The Snaith–Hamilton Pleasure Scale (SHAPS) is a measure of anhedonia used to verify inclusion criteria. It is a well-validated 14-item self-report questionnaire that is administered by computer.

3) DSM diagnoses will be made using the SCID5, a semi-structured patient interview, and will be used to verify inclusion criteria

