To control for nonspecific factors in BATA including clinician contact, MBCT will be administered in an individual format. MBCT for individual treatment is empirically supported for a number of forms of psychopathology. Individualized adaptations of MBCT share primary components of the traditional program, including instruction and in-session practice of meditative exercises, didactics, and home practice. MBCT will be comprised of 15 weekly 45-minute sessions. Sessions will begin with practice and discussion of a mindfulness meditation exercise, and then include: discussion of home practice, introduction to a new exercise and/or psychoeducational topic, and explanation of home practice for the coming week. Initial sessions will focus on practice and discussion of core meditation exercises to build mindfulness skills. Later sessions will focus on generalizing learned skills to cope with stressors and mood shifts. Psychoeducational content will center on identifying connections between negative thoughts, emotions, and sensations, recognizing triggers of emotional events, and developing an "action plan" to reduce stress-related symptoms. At the end of each session, participants will receive handouts that summarize the meditative exercise and/or psychoeducational content covered each week. Participants will also be asked to practice meditation exercises at home for 30 minutes each day and track practice time. Homework and logging are included to control for homework and monitoring components of BATA. Participants will receive guided meditation CDs to aid in home practice. Adherence will be monitored by tracking attendance; compliance of home practice will be monitored by evaluating frequency and duration of practice on weekly homework logs.

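### The physiological-noise step in Section 5 is tied to the structural scans, so as written it cannot correct the ventral tegmental BOLD signal it is meant to improve

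*Combined protocol and SAP*

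**What the plan says.** The relevant text is in Section 5, item 1 of the combined protocol and SAP, which describes acquisition and analysis of the fMRI data.

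- **Aim of the sentence.** It opens with "To optimize BOLD signal coverage in the ventral" tegmental area.
- **First means.** For this purpose "we will acquire high-resolution T1-weighted images with 1x1x1 mm voxel size to allow for precise registration".
- **Second means.** The study also "will use cardiac and respiratory gated imaging during the acquisition of structural scans to address pulsatile artifacts using retrospective corrections", and the tool is named: "retrospective corrections implemented with the FSL PNM toolbox".
- **Primary regions.** Earlier in the item, "Analyses of fMRI target engagement will focus on activation in the right CN during reward anticipation, the rACC during reward outcomes". The bilateral amygdala is added for the threat task.
- **How the endpoint is obtained.** "Hypotheses will be evaluated with a ROI approach whereby signal intensities are extracted from ROIs for the relevant task contrasts"; these are contrasts between trial types in the reward (MID) and threat tasks.
- **Place of the VTA.** It is listed among the further reward regions to be examined in the whole-brain follow-up, not among the ROIs that carry the hypotheses.

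Sections 4.1 and 4.2 list structural and functional scans as separate acquisitions within a scan session. Section 5 places the sessions at weeks 0, 8, 12 and 15.

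**The concern.** The purpose and the means in this sentence do not match. The purpose is BOLD signal, which exists only in the functional time series. The means is cardiac and respiratory gating during a structural acquisition, which yields an anatomical image and no BOLD series. The sentence also joins two different techniques: gating, which controls when data are acquired, and retrospective correction, which models physiological fluctuation in data already acquired.

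The practical stake is that traces not recorded during a functional run cannot be recovered later. Scanner staff who follow the text literally would collect physiological data in the wrong acquisition at every visit. The analyst would then have nothing to feed to PNM for the task runs. A publication that repeated the sentence would also describe a correction that had not been made.

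**Working it through.** No arithmetic applies, because the plan states no figure on this point. The check sets the statements side by side.

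1. **What the correction needs.** Retrospective modelling of cardiac and respiratory noise assigns each volume of a time series a position in the pulse and breathing cycles. That requires traces recorded at the same time as the series.
2. **What the plan would record.** Section 5 ties the cardiac and respiratory acquisition to the structural scans. Sections 4.1 and 4.2 treat these as distinct from the functional scans. A trace from one acquisition says nothing about the phase of the pulse or breath in another.
3. **What the structural images are for.** The same sentence gives the T1 images their own role, registration. Better registration helps to locate the VTA in the functional data, but it removes no noise from that region's time series.
4. **Whether another section fills the gap.** I read every other place that deals with scanning or fMRI analysis: the synopsis, Sections 3.1, 4.1, 4.2 and 5.3, and Sections 6.1, 6.4 and 6.5. None mentions pulse or respiration recording, and none mentions physiological regressors. The rest of Section 5 names FSL as the preprocessing software and a head-motion comparison using framewise displacement, but no physiological-noise model.
5. **Which results are touched.** The correction is offered for the VTA, a follow-up region. The primary endpoint in Sections 6.1 and 6.4 is right caudate and rostral anterior cingulate activation. In Section 5 these are ROI values for which "signal intensities are extracted from ROIs for the relevant task contrasts". No physiological correction is stated for them anywhere, so the failure of this step withdraws nothing that was promised for them.
6. **Size.** To turn uncorrected noise into lost precision one would need its share of the variance of the pre-to-post change, or a temporal signal-to-noise or test-retest figure. The documents give none of these.

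**The case against.** **A drafting slip.** Both the BOLD aim and the choice of PNM point to functional data, so *structural* may simply stand where *functional* was meant. The documents are silent on recording in the functional runs; they do not rule it out. This is plausible, and it is one reason the point is minor. It does not remove the point, because staff work from the text and the text names the wrong acquisition.

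**Gating the structural scan may have its own use.** It might sharpen the anatomical image and so help registration. Even if it does, that would not make a retrospective correction of the BOLD signal possible.

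**Stronger readings that the documents do not support.** Three are tempting.

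- A reader might infer that a promised safeguard for the primary endpoint fails. It does not: the sentence is about the VTA. Physiological regressors for the caudate and cingulate ROIs would be an improvement, not the repair of a stated step.
- A reader might infer a bias between arms, since Section 1.2 says of the comparator that "Participants will also be asked to practice meditation exercises at home for 30 minutes each day", and meditation might alter breathing or pulse in the scanner. Nothing in the documents shows that it would. The endpoint is also a contrast between trial types within a run, so a general change in breathing would have to track trial type to bias it directly. That is speculation.
- A reader might attach a gain in power to the correction. That needs an assumed noise share with no source in the documents, and it would ignore the degrees of freedom that the regressors use. I give no figure.

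**Conclusion.** The concern holds in a limited form. As written, the step cannot correct BOLD signal in the VTA, which is its stated purpose, and it supplies no physiological correction for the primary ROIs, for which none was promised. This is a stated method that cannot do its job, not merely a missing detail. Its reach is a follow-up region, and the effect on precision is unknown. Severity: minor.

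The conclusion rests on reading the sentence as printed, and on the requirement that traces be simultaneous with the series being corrected. If the site already records traces in the functional runs, the defect is one of wording only. The text should still be corrected.

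**What to change.** Replace the clause on gated structural imaging in Section 5, item 1 with: *cardiac and respiratory traces will be recorded during every functional run at each scan, and PNM-derived regressors will be entered in the first-level model.* Apply this in the same way to the ROI and whole-brain analyses, so that the two rest on the same model. Add a rule, fixed before the data are analysed, for runs whose traces are missing or unusable. The T1 acquisition for registration can stay as it is.

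If traces will not be recorded in the functional runs, delete the statement that PNM addresses pulsatile artefacts.

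The cost is some first-level degrees of freedom, plus the work of checking traces and handling bad ones. Cardiac and respiratory monitoring is already planned, though the text places it only in the structural scans. Recording during runs that take place anyway should add no scan time. The change matters most before scanning starts, since it cannot be applied to runs already acquired without traces.
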